6. CONCOMITANT THERAPIES AND OTHER RESTRICTIONS

6.1. Concomitant Therapies

Paracetamol/acetaminophen (maximum 2 g/day for up to 3 consecutive days) is an acceptable concomitant medication.

Subjects will refrain from participation in any other investigational study drug trial in which receipt of any investigational drug occurs within 5 half-lives (if known) or 30 days, whichever is longer, prior to first dose administration (Day 1).

All prescription/nonprescription and over-the-counter medications (including herbal products, natural or herbal supplements, except for paracetamol/acetaminophen as referenced above) are prohibited for 14 days prior to dose administration (Day 1) and through EOT or ET, unless deemed acceptable by the Investigator (or designee) and Sponsor. This includes but is not limited to: moderate or strong CYP3A4 and/or CYP3A5 inhibitors or inducers (including herbal products such as St, John's wort), strong P-gp inhibitors, proton pump inhibitors, antacids, H₂-receptor antagonists, and drugs that prolong QT/QTc interval.

Any medication taken by a subject during the course of the study, including details of its dosage, administration, and the reason for its use, will be documented in the eCRF.

The administration of any concomitant medication during the study is prohibited without prior approval of the Investigator (or designee) and Sponsor, unless its use is deemed necessary in a medical emergency. In this case, the use of the concomitant medication will be reported as soon as is practical.

6.2. Diet, Fluid, and Activity Control

While confined at the CRU, subjects will receive a standardized high fiber diet at scheduled times that do not conflict with other study-related activities. Pitted prunes or prune juice may be given on an as-needed basis to aid in normal bowel function and will not be considered a concomitant medication.

Subjects are required to refrain from use of tobacco, smoking cessation products, and nicotine-containing products within 3 months prior to Screening through EOT or ET.

Consumption of foods or beverages containing grapefruit/grapefruit juice or Seville oranges or its juice within 7 days prior to Check-in (Day -1) and through EOT or ET will not be allowed unless deemed acceptable by the Investigator (or designee) and Sponsor.

Consumption of alcohol- or caffeine-containing foods or beverages within 72 hours prior to Check-in (Day -1) and through EOT or ET will not be allowed unless deemed acceptable by the Investigator (or designee) and Sponsor.

Subjects will refrain from strenuous exercise from 5 days prior to Check-in (Day -1) and during the period of confinement at the CRU and will otherwise maintain their normal level of physical activity through EOT or ET (ie, should not begin a new exercise program or participate in any unusually strenuous physical exertion).

Fasting requirements in relation to dosing are described in Section 3.1 and Section 5.2. Fasting requirements in relation to collection of blood for clinical laboratory evaluations are described in Section 7.2.2 and Appendix 4.

7. STUDY ASSESSMENTS AND PROCEDURES

7.1. Pharmacokinetic Assessments

7.1.1. Pharmacokinetic, Total Radioactivity, and Metabolite Profiling Blood Sample Collection and Processing

Blood samples for PK analysis for determination of LOXO-305, total radioactivity, and metabolite profiling and identification in Part 1 and for LOXO-305, [¹⁴C]-LOXO-305, and total radioactivity in Part 2 will be collected at the times indicated in the Schedule of Assessments (Appendix 4). Blood samples will be collected from the contralateral arm to the arm/hand used for IV dose administration. Procedures for collection, processing, and shipping of blood samples will be detailed in a separate document.

Processing, storage, and shipping instructions for PK, total radioactivity, and metabolite profiling and identification blood samples will be provided in a separate Laboratory Manual. The number of blood samples and total blood volume required for PK, total radioactivity, and metabolite profiling and identification testing is presented in Appendix 3.

7.1.2. Pharmacokinetic, Total Radioactivity, and Metabolite Profiling Urine and Feces Collection and Processing

Urine will be collected over the time intervals indicated in the Schedule of Assessments in Appendix 4 for determination of total radioactivity and metabolite profiling and identification for Part 1 and for [¹⁴C]-LOXO-305 concentration and total radioactivity in Part 2. Procedures for collection, processing, and shipping of urine collections will be detailed in a separate document.

Feces will be collected over the time intervals indicated in the Schedule of Assessments in Appendix 4 for determination of total radioactivity in Parts 1 and 2, metabolite profiling and identification for Part 1 (where possible), and for measurement of [¹⁴C]-LOXO-305 in Part 2. If possible, a single baseline fecal sample will be collected from after Check-in on Day -1 until predose on Day 1. Procedures for collection, processing, and shipping of feces collections will be detailed in a separate document.

7.1.3. Vomitus Sample Collection

In Part 1, for subjects experiencing emesis within 4 hours following oral dosing, vomitus will be collected. Attempts will be made to collect vomitus from subjects experiencing emesis after 4 hours postdose. All vomitus collected will be stored for possible analysis as deemed appropriate.

7.1.4. Analytical Methodology

In Parts 1 and 2, plasma concentrations of LOXO-305 will be determined using a validated bioanalytical method.

In Part 1, total radioactivity in plasma, whole blood, urine, and feces will be determined with liquid scintillation counting (LSC). Profiling and identification of metabolites in plasma, urine, and, where possible, feces will be conducted using standard laboratory procedures.

In Part 2, concentrations of [¹⁴C]-LOXO-305 in plasma, urine, and feces will be determined using high performance liquid chromatography fractionation followed by AMS. Concentrations of total radioactivity in plasma, urine and feces will be determined using AMS and/or LSC. Specifics of the analytical methods will be provided in separate documents.

7.2. Safety and Tolerability Assessments

Safety evaluations may be repeated at the discretion of the Investigator (or designee) or Sponsor.

Every effort will be made to schedule and perform the procedures in accordance with the nominal time, giving considerations to appropriate posture conditions, practical restrictions, and any other procedures to be performed at the same timepoint. The order of priority for scheduling procedures around a timepoint is (in descending order of priority):

- dosing
- PK, total radioactivity, and metabolite profiling and identification blood sampling
- start and end of urine and fecal collections (for drug assay)
- vital sign measurements
- 12-lead ECGs
- blood and urine samples for clinical laboratory evaluations
- physical examination.

7.2.1. Adverse Events

Adverse event definitions; assignment of severity, causality, action taken, and outcome; and procedures for reporting SAEs are detailed in Appendix 1.

Subjects will be asked a non-leading HDYF? question such as "Have there been any changes in your health status since Screening/since you were last asked?" at the timepoints specified

in Appendix 4 (ie, at Screening [after the ICF is signed], at Check-in [Day -1], at each postdose vital sign measurements, and at an appropriate time for all other days). Subjects will also be encouraged to voluntarily report AEs occurring at any other time through the EOS.

Adverse events, whether volunteered, identified by the subject's responses to HDYF? inquiries, or noted on physical examination, ECG, vital sign measurements, or clinical laboratory evaluations, will be recorded throughout the study (ie, from signing of the ICF until EOS [or ET if the subject discontinues from the study and does not complete a Follow-up Phone Call]), either as subject medical history (if the event is reported as beginning prior to signing of the ICF or if the event occurs prior to study drug administration on Day 1 and is assessed as not related to study procedures by the Investigator [or designee]) or as AEs (if the event occurs after signing of the ICF but prior to study drug administration on Day 1 and is assessed as related to study procedures by the Investigator [or designee], or if the event occurs after study drug administration on Day 1 through EOT or ET regardless of relationship to study drug). From EOT or ET through EOS, only AEs assessed as related to study drug by the Investigator (or designee) are to be reported. All SAEs that develop from the time of ICF signing until EOS (or ET, if the subject discontinues from the study and does not complete a Follow-up Phone Call) are to be reported.

Unless a subject withdraws consent or is withdrawn from the study and does not complete the Follow-up Phone Call, all subjects must be followed until EOS. Subjects with AEs that are assessed as related to study drug by the Investigator (or designee) which are ongoing at EOS may continue to be followed until the symptoms or value(s) return to normal, or acceptable levels, as judged by the Investigator (or designee) and confirmed by the Sponsor. The Investigator (or designee) should use appropriate judgment in ordering additional tests as necessary to monitor the resolution of events. The Sponsor may request that additional safety tests be performed.

Subjects will receive a Follow-up Phone Call 7 days (\pm 2 days) after EOT or ET to determine if any SAE or drug-related AE has occurred since the EOT or ET visit.

At all times, a subject may be required to remain at the CRU for longer at the discretion of the Investigator (or designee).

Any event that meets the criteria of a suspected unexpected serious adverse reaction (SUSAR) will be reported to the Institutional Review Board (IRB) according to CRU policy by the Investigator (or designee) and to regulatory authorities by the Sponsor (or Sponsor designee) according to regulatory authority requirements. Refer to Reference Safety Information (RSI) in the current IB¹ for LOXO-305 for additional safety information.

7.2.2. Clinical Laboratory Evaluations

Clinical laboratory evaluations (clinical chemistry panel [fasted at least 8 hours; at EOT and ET subjects are not required to be fasted prior to clinical laboratory evaluations], coagulation parameters, hematology panel, TSH [Screening only], HbA1c [Screening only], glomerular filtration rate [Screening and Check-in (Day -1)] and UA) will be collected at the timepoints specified in Appendix 4.

Screens for HCV antibody, HBV core antibody, HBsAg, and HIV antibody will be performed at Screening.

Testing for COVID-19 via PCR (or equivalent) will be performed at the timepoints specified in Appendix 4. Testing for COVID-19 may also be conducted periodically during the subject's CRU confinement, at the discretion of the Investigator (or designee). Further details regarding COVID-19 testing (including procedures who test positive at any time throughout CRU confinement) are specified in a separate document.

A urine drug screen for selected drugs of abuse (including cotinine and alcohol) will be performed at Screening and repeated at Check-in (Day -1) for all subjects.

The number of blood samples and total blood volume required for clinical laboratory evaluations is presented in Appendix 3. A list of the specific evaluations is in Appendix 2.

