4.2. Check-in Procedures (Day -1)

At Check-in (Day -1), subjects will report to the CRU and the following procedures will be performed:

- 1. Review of inclusion/exclusion criteria
- 2. Interim medical history, including concomitant medication(s)
- 3. Weight and BMI
- 4. Complete physical examination (Section 7.2.5)
- 5. 12-lead ECG measured after the subject has been resting in the supine position for at least 10 minutes (Section 7.2.4)
- 6. Vital sign measurements (including oxygen saturation, oral temperature, respiratory rate, and supine BP and pulse rate [measured after the subject has been supine for at least 5 minutes]; Section 7.2.3)
- 7. HDYF? inquiry, AE, SAE, and concomitant medication evaluations (Section 7.2.1)
- 8. Clinical laboratory evaluations (Section 7.2.2; clinical chemistry panel [fasted at least 8 hours], coagulation parameters, hematology panel, and UA; Appendix 2)
- 9. Screen for COVID-19 via PCR or equivalent (Appendix 2)
- 10. Estimated glomerular filtration rate (Appendix 2)
- 11. Screen for selected drugs of abuse, including cotinine and alcohol (Appendix 2)
- 12. Compliance with concomitant medications and exclusionary restrictions (Section 6).

For subjects to continue their participation in the study, the inclusion/exclusion criteria must continue to be met at Check-in (Day -1 [as appropriate; #1, Section 4.2]). In addition, continued compliance with concomitant medication and other restrictions will be verified.

The Sponsor will review medical history and all screening evaluations for potential subjects prior to enrollment. Prior to dosing, the Sponsor will provide approval of subjects selected for enrollment by the Investigator (or designee).

Subjects who meet all the inclusion criteria and for whom none of the exclusion criteria apply will be eligible to be enrolled into the study. Safety evaluations may be repeated at the discretion of the Investigator (or designee) or Sponsor.

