- n. Urine samples for determination of total radioactivity and metabolite profiling/characterization will be collected from 12 hours prior to dose administration (-12 to 0 hours predose); from 0 to 6, 6 to 12, and 12 to 24 hours; and for 24-hour intervals up to and including 264 hours postdose (Day 12). If a subject does not meet the discharge criteria on Day 12, additional urine samples will be collected at 24-hour intervals until the Day of Clinic Discharge (EOT) or ET.
- o. If possible, a single baseline fecal sample will be collected from after Check-in on Day -1 until just prior to dose administration on Day 1. Postdose fecal samples for determination of total radioactivity and metabolite profiling/characterization will be collected from 0 to 24 hours postdose and for 24-hour intervals from Day 2 up to and including 264 hours postdose (Day 12). If a subject does not meet the discharge criteria on Day 12, additional fecal samples will be collected at 24-hour intervals until discharge from the CRU (EOT) or ET.

Protocol	CONFIDENTIAL
Covance Study: 8419667	Protocol Reference: LOXO-BTK-20007

- p. Clinical chemistry panel (fasted for at least 8 hours), coagulation parameters, hematology panel, and UA will be performed. On the day prior to EOT (if the subject completes the study) or ET, subjects are not required to be fasted prior to clinical laboratory evaluations.
- q. Clinical laboratory evaluations will be performed on Day 14 (if a subject is in the CRU), Day 19 (if the subject is in the CRU), and on the day prior to Clinic Discharge (EOT) or on the day of ET. Clinical laboratory evaluations will be performed on the day prior to subject release from the CRU if the subject completes the study (EOT). Clinical laboratory evaluations will be performed on the day of subject release from the CRU if the subject terminates early (ET).
- r. Testing for COVID-19 will be conducted at a minimum at Screening, Check-in (Day -1), and predose on Day 1. Testing for COVID-19 may also be conducted periodically during the subject's CRU confinement, at the discretion of the Investigator (or designee). Tests will be performed by rapid polymerase chain reaction or equivalent.
- s. Drugs of abuse urine test, including cotinine and alcohol. Results from the drugs of abuse tests will be used to determine subject eligibility per the inclusion/exclusion criteria.

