- n. If possible, a single baseline fecal sample will be collected from after Check-in on Day -1 until just prior to oral dose administration on Day 1. Postdose fecal samples for determination of [¹⁴C]-LOXO-305 and total radioactivity will be collected from 0 (time of oral dose) to 12 hours postdose relative to the start of IV dose administration; from 12 to 24 hours postdose relative to the start of IV dose administration; and for 24-hour intervals up to and including 192 hours postdose (Day 9 [EOT]), relative to the start of IV dose administration.
- o. Clinical chemistry panel (fasted for at least 8 hours), coagulation parameters, hematology panel, and UA will be performed. On Day 8 (if the subject completes the study) or at ET, subjects are not required to be fasted prior to clinical laboratory evaluations.
- p. Testing for COVID-19 will be conducted at a minimum at Screening, Check-in (Day -1), and predose on Day 1. Testing for COVID-19 may also be conducted periodically during the subject's CRU confinement, at the discretion of the Investigator (or designee). Tests will be performed by rapid polymerase chain reaction or equivalent.
- q. Drugs of abuse urine test, including cotinine and alcohol. Results from the drug of abuse tests will be used to determine subject eligibility per the inclusion/exclusion criteria.
- r. Prior and concomitant medication administration will be recorded beginning at informed consent. In addition, all Investigator-approved medications taken by a subject within 14 days prior to study drug administration for prescription medications and non-prescription medications, will be recorded on the subject's electronic Case Report Form.

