- s. EOT is defined as when the subject is released from the CRU following completion of all assessments through Day 9 (EOT). ET is defined as when the subject is released from the CRU if the subject terminates the study early. Vital sign measurements, ECG, and abbreviated physical examination results are to be available for review by the Investigator (or designee) prior to subject release from the CRU on Day 9 (EOT) or ET. Clinical laboratory results for clinical chemistry, hematology, coagulation, and UA are to be available for review by the Investigator (or designee) prior to subject release from the CRU at the EOT visit and prior to subject release from the CRU at the EOT visit and prior to subject release from the CRU at the EOT visit and prior to subject release from the CRU at the EOT visit and prior to subject release from the CRU at the EOT visit and prior to subject release from the CRU at the EOT visit and prior to subject release from the CRU at the EOT visit and prior to subject release from the CRU at the EOT visit and prior to subject release from the CRU at the EOT visit and prior to subject release from the CRU at the EOT visit and prior to subject release from the CRU at the EOT visit and prior to subject release from the CRU at the EOT visit and prior to subject release from the CRU at the EOT visit and prior to subject release from the CRU at the EOT visit and prior to subject release from the CRU at the EOT visit and prior to subject release from the CRU at the EOT visit and prior to subject release from the CRU at the EOT visit and prior to subject release from the CRU at the EOT visit and prior to subject release from the CRU at the EOT visit and prior to subject release from the CRU at the EOT visit and prior to subject release from the CRU at the EOT visit and prior to subject release from the CRU at the EOT visit and prior to subject release from the CRU at the EOT visit and prior to subject release from the CRU at the EOT visit and prior to subject release from the CRU at the EOT visit
- t. Clinical laboratory evaluations will be performed on the day prior to subject release from the CRU (Day 8) if the subject completes the study (EOT). Clinical laboratory evaluations will be performed on the day of subject release from the CRU if the subject terminates early (ET).

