### **8.1.1. Calculation of the Summary Statistics**

For continuous data the following rules will be applied:

- Missing values will not be imputed, unless specifically stated otherwise.
- Unrounded data will be used in the calculation of summary statistics.
- If the number of subjects with valid observations (n) <3, summary statistics will not be calculated, with the exception of n, minimum, and maximum.
- As ET data is not associated with any scheduled timepoint, it will be excluded from all calculations of summary statistics.
- Post dose repeats and unscheduled assessments will not be included in calculation of summary statistics.

For categorical data the following rules will be applied:

- If the categories of a parameter are ordered (eg, AE severity), all categories between the possible minimum and maximum categories will be included, even if n = 0 for a given category. If the categories are not ordered (eg, race), only those categories for which there is at least 1 subject represented will be included.
- Missing values will not be imputed, with the exception of AEs where the ‘worst-case’ approach will be taken (see [Section 8.6.1](#)), or unless specifically stated otherwise. A ‘missing’ category will be included for any parameter for which information is missing. This will ensure that the population size totals are consistent across different parameters.

All protocol deviations and data issues (eg missing data, out of protocol window) that occur during the study, including those related to COVID-19, will be considered prior to database lock for their severity/impact on how the data will be displayed.

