### **8.1.3. Definitions of Baseline and Change from Baseline**

Baseline value is defined as the last non missing measurement before administration of LOXO-305 in each part of the study.

In general, baseline for Part 1 and Part 2 refers to the pre-dose value collected on Day 1. For laboratory tests, baseline is the value collected on Day -1.

If the date/time of the value is incomplete or missing, it will be excluded from the baseline calculation, unless the incomplete date/time indicates the value was recorded prior to dosing of LOXO-305 in each part of the study.

Individual changes from baseline will be calculated by subtracting the individual subject's baseline value from the value at the timepoint. The mean change from baseline will be defined as the mean of the individual changes from baseline for all subjects.

See Section [8.1.2](#) for more detail on handling repeat and unscheduled readings in the calculations.

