### **8.6.2. Clinical Laboratory Parameters**

All clinical laboratory parameters, with changes from baseline, will be listed; any value outside the clinical reference range will be flagged, and whether the out of range value was deemed clinically significant or not clinically significant will be indicated. Separate listings will be provided for any parameter for which there is any individual subject value outside the respective clinical reference range.

The observed results and change from baseline for clinical chemistry, hematology, and coagulation parameters will be summarized descriptively by study part and timepoint.

Values recorded as  $< x$ ,  $\leq x$ ,  $> x$ , or  $\geq x$  will be displayed in the listings as recorded. For the derivation of listing flags, calculation of summary statistics, and presentation in the figures,  $< x$  and  $\leq x$  values will be set to 0 whereas  $> x$  and  $\geq x$  values will be set to  $x$ .

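### The last scheduled chemistry panel may be drawn unfasted, but its change from a fasted baseline is summarised with no account of fasting state

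*Protocol*

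**What the plan says.** **Baseline.** Protocol 4.2 lists the Check-in laboratory work as "clinical chemistry panel [fasted at least 8 hours], coagulation parameters, hematology panel, and UA; Appendix 2". SAP 8.1.3 then states: "For laboratory tests, baseline is the value collected on Day -1". The baseline for change scores is therefore a fasted sample.

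**Post-dose panels.** The Appendix 4 schedules place laboratory evaluations on Days 4 and 7 in both parts and on Day 9 in Part 1. Part 1 subjects still resident are also sampled on Days 14 and 19. The chemistry footnotes (p in Part 1, o in Part 2) require at least 8 hours of fasting.

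**The exception.** Section 7.2.2 says that "at EOT and ET subjects are not required to be fasted prior to clinical laboratory evaluations". Part 1 footnote p words it differently: "On the day prior to EOT (if the subject completes the study) or ET, subjects are not required to be fasted". Part 2 footnote o has: "On Day 8 (if the subject completes the study) or at ET, subjects are not required to be fasted". Part 1 footnote q and Part 2 footnote t confirm that completers are sampled the day before release and early terminators on the day of release.

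**Analysis.** SAP 8.6.2 states: "The observed results and change from baseline for clinical chemistry, hematology, and coagulation parameters will be summarized descriptively by study part and timepoint". Early-termination values are dealt with in SAP 8.1.1: "As ET data is not associated with any scheduled timepoint, it will be excluded from all calculations of summary statistics". No such rule covers completers' unfasted values. Neither document mentions recording fasting status at the draw. The case report form and table shells, to which the SAP refers, are not among the documents.

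**The concern.** A change score is easiest to read when both samples are taken under the same conditions. Here the first sample is fasted and the last one need not be. Appendix 2 includes glucose, iron and triglycerides, which can respond to a recent meal, so a difference at the last draw may mix food with drug.

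Each part has six subjects and no control group, so change from baseline is the only summary comparison for these analytes. No later laboratory draw is scheduled that could settle a doubtful value. A meal could also push a value outside the reference range, which SAP 8.6.2 flags and lists separately.

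For completers the mismatch looks avoidable. They are still confined on the day of the draw, and Protocol 6.2 has meals served at scheduled times that do not conflict with study activities.

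**Working it through.** The documents give no figure to reproduce, so the check is a comparison of the text followed by simple algebra.

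**Step 1: fasting state by draw.**

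| Draw | Fasting rule | In change-from-baseline summary? |
|---|---|---|
| Day -1 (baseline) | At least 8 h | Reference value |
| Days 4 and 7; Day 9 in Part 1 | At least 8 h | Yes |
| Days 14 and 19, Part 1, if resident | At least 8 h, unless also the day before discharge (Step 2) | Yes |
| Completers' last draw (Day 8 in Part 2; day before discharge in Part 1) | Waived | Yes |
| Early termination | Waived | No (SAP 8.1.1) |

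The problem in the summaries therefore comes only from completers' last draw. Hematology, coagulation and urinalysis carry no fasting condition and are not affected.

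**Step 2: consistency of the waiver.** Appendix 4 defines EOT as the release from the unit (Part 1 footnote u, Part 2 footnote s). Read literally, 7.2.2 waives fasting at a moment when completers have no planned draw, while the footnotes waive it the day before. In Part 1, discharge on Day 12 to Day 22 puts the draw on Day 11 to Day 21. It can therefore fall on Day 14 or Day 19, and the text does not say which fasting rule then applies.

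**Step 3: can a recheck repair the summary?** Protocol 7.2 allows safety evaluations to be repeated. SAP 8.1.2, however, classes any additional laboratory value as unscheduled, uses the original post-dose value and excludes the rest. A fasted recheck would be listed but would not change the table.

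**Step 4: size.** Let k of 6 subjects be unfasted and let a meal add d to the analyte in each of them. Then

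observed mean change = mean change had all been fasted + (k/6) × d.

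The table also shows how many values would remain if unfasted ones were dropped. SAP 8.1.1 suppresses everything except n, minimum and maximum when n < 3.

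| k | Shift | n left if dropped (6 − k) | Mean still reported? |
|---|---|---|---|
| 0 | 0 | 6 | Yes |
| 1 | 0.17 d | 5 | Yes |
| 2 | 0.33 d | 4 | Yes |
| 3 | 0.50 d | 3 | Yes |
| 4 | 0.67 d | 2 | No |
| 5 | 0.83 d | 1 | No |
| 6 | d | 0 | No |

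The documents give neither k nor d. The formula assumes that all six subjects contribute to one end-of-treatment timepoint and that d is the same for each.

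**The case against.** The strongest reply is that a reader can usually recognise a meal effect from the schedule itself. In Part 2 the waived Day 8 panel comes one day after a fasted Day 7 panel, and both parts have fasted panels earlier, when exposure is higher. Protocol 1.3.2 gives a half-life of about 20 hours, estimated in patients with an imputed 24-hour sample. On that figure, Day 8 is about 168/20 = 8.4 half-lives after the oral dose (0.5^8.4, about 0.3% remaining). The earliest Part 1 final draw, Day 11, is about 240/20 = 12 half-lives (about 0.02%). A drug effect first appearing then is a weak rival explanation. This stands, subject to the half-life being an approximate parent-drug estimate from another population. A reader might infer that a meal effect and a drug effect could not be told apart; the earlier fasted panels do not support so strong a reading.

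It also stands that the text is permissive. Subjects need not be fasted, but nothing says they will be fed, so k may be 0 and a shift is possible rather than certain.

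Out-of-range flags are less troubling than they look. SAP 8.6.2 pairs each flag with an indication of clinical significance, and Protocol Appendix 1 counts laboratory abnormalities as adverse events only when they are clinically relevant.

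Finally, safety is a secondary objective, the analysis is descriptive, and no decision rule depends on these means. That limits the importance of the point but does not justify comparing samples taken under different conditions when the difference could be avoided.

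**Conclusion.** The point holds as a minor one. The plan permits an unfasted final chemistry panel for completers, compares it with a fasted baseline, and has no rule to separate the two states. The possible shift in the mean for a meal-sensitive analyte is (k/6) × d, from nothing to the full meal effect. No absolute size can be given from the documents.

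A reader might also infer that the last safety timepoint as a whole is compromised. It is not: this is the last scheduled laboratory draw, and only meal-sensitive chemistry analytes are affected. ECG, vital signs and physical examination follow on the day of discharge, and a follow-up call comes later. Early-termination values do not enter the summaries at all.

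The conclusion assumes that fasting status is not already captured in the case report form or handled in the table shells.

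**What to change.** 1. In Protocol 7.2.2 and Appendix 4 (Part 1 footnote p, Part 2 footnote o), apply the 8-hour fast to the planned end-of-treatment chemistry draw for completers. Keep the waiver for unplanned early termination.
2. Use the same reference point throughout: reconcile EOT in 7.2.2 with the day before EOT and Day 8 in the footnotes. State which fasting rule applies when the Part 1 final draw falls on Day 14 or Day 19.
3. In Part 1, where discharge depends on recovery results and may not be known the evening before, record fasting status at the draw. Do the same in both parts if the waiver stays. Add to SAP 8.6.2 that unfasted values of named meal-sensitive analytes are flagged or presented separately.
4. Do not drop the unfasted values instead. With four or more of six unfasted, the n < 3 rule would suppress the mean.

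The cost is one more scheduled fasted draw for subjects already confined, or one recorded field and a flag in the tables.
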